4.2 Exclusion Criteria

All subjects meeting any of the exclusion criteria at baseline will be excluded from study.

- 4.2.1 Is receiving systemic steroid therapy or any other form of immunosuppressive therapy for autoimmune side effects related to previous use of immunotherapies for melanoma. Exceptions include episodic (up to 7 days) use of systemic steroids for common conditions while on study treatment (e.g. COPD exacerbation, poison ivy), use of corticosteroids as replacement doses for adrenal or pituitary insufficiency.
- 4.2.2 Has a known history of tuberculosis (Bacillus Tuberculosis) or human immunodeficiency virus (HIV 1/2 antibodies).
- 4.2.3 Hypersensitivity to pembrolizumab or any of its excipients. Allergy to benzamide or inactive components of entinostat.
- 4.2.4 Has known history of biopsy-proven (non-infectious) pneumonitis that required systemic steroids, or any evidence of current pneumonitis.
- 4.2.5 Conditions that would preclude adequate absorption of oral medications (malabsorption, significant nausea and vomiting, resection of >100 -cm of proximal small bowel, resection of >200 -cm of distant small bowel).
- 4.2.6 Has a history or current evidence of any condition, therapy, or laboratory abnormality that might confound the results of the trial, interfere with the subject's participation for the full duration of the trial, or is not in the best interest of the subject to participate, in the opinion of the treating investigator, including but not limited to:
- i.** Myocardial infarction or arterial thromboembolic events within 6 months prior to screening or severe or unstable angina, New York Heart Association (NYHA) Class III or IV disease, or a QTc interval > 470 msec,
 - ii.** Active infection requiring systemic antibiotic therapy by the first day of entinostat treatment,
 - iii.** Known psychiatric or substance abuse disorders that would interfere with cooperation with the requirements of the trial.

- 4.2.7 If female, is pregnant or breastfeeding, or, if male, expecting to conceive or father children within the projected duration of the trial, starting with the pre-screening or screening visit through 120 days after the last dose of trial treatment.
- 4.2.8 Known active hepatitis B (e.g., hepatitis B surface antigen-reactive) or hepatitis C (e.g., hepatitis C virus ribonucleic acid [qualitative]). Patients with past hepatitis B virus (HBV) infection or resolved HBV infection (defined as the presence of hepatitis B core antibody [HBc Ab] and absence of HBs Ag) are eligible. HBV DNA test must be performed in these patients prior to study treatment if known history of viral hepatitis. Patients positive for hepatitis C virus (HCV) antibody are eligible, only if polymerase chain reaction is negative for HCV RNA.
- 4.2.9 Has received a live vaccine within 30 days of planned start of study therapy.
Note: Seasonal influenza vaccines for injection are generally inactivated flu vaccines and are allowed; however intranasal influenza vaccines (e.g., Flu-Mist®) are live-attenuated vaccines and are not allowed.
- 4.2.10 History of prior malignancy, with the exception of the following:
- Non-melanoma skin cancers, non-invasive bladder cancer, and carcinoma *in situ* of the cervix,
 - Prior history of prostate cancer provided the patient is not undergoing active systemic treatment other than hormonal therapy and has documented PSA that is undetectable (<0.2ng/mL),
 - Papillary thyroid cancer, even if patients may have just completed thyroidectomy within the last 2 years, have not received adjuvant radioactive iodine therapy, and were only recently diagnosed with asymptomatic papillary thyroid cancer and their surgery is pending,
 - Chronic lymphocytic leukemia (CLL) provided patient has isolated lymphocytosis (Rai stage 0) and does not require systemic treatment [for “B” symptoms, Richter’s transformation, lymphocyte doubling time (<6 months), lymphadenopathy or hepatosplenomegaly],
 - Lymphoma, hairy-cell leukemia, or myelodysplasia, provided that patient is not on active systemic treatment and is in complete remission, as evidenced by PET/CT scans and bone marrow biopsies for at least 3 months,
 - History of any other malignancy provided patient has completed therapy and is free of disease for ≥ 2 years. If patient had other malignancy within the last 2 years from which he, or she, may have been completely cured by surgery alone, he may be

considered to be enrolled on condition that the risk of development of distant metastatic disease based on the most recent AJCC staging system is less than 30%.

4.2.11 Has known active (i.e. previously untreated) parenchymal central nervous system (CNS) metastases that are symptomatic, and/or more than one lesion with the largest diameter being > 5-mm and/or require antiepileptic drugs or systemic corticosteroids for management of intracranial symptoms. Patients with carcinomatous meningitis are also excluded. Exceptions are:

Subjects with previously treated brain metastases provided they are stable (i.e. without evidence of progression by brain MRI or head CT with IV contrast) for at least 2 weeks prior to the first dose of entinostat. Any neurologic symptoms must have returned to baseline, and have no evidence of new or enlarging brain metastases, and are not using ongoing systemic corticosteroids for management of intracranial symptoms for at least 7 days prior to first dose of entinostat,

Patients with active (i.e. not treated with stereotactic radiosurgery), single, asymptomatic, up to 5-mm in largest diameter brain metastases (measured either by brain MRI with IV contrast or head CT with IV contrast measuring within 2 weeks prior to the first dose of entinostat).

[figure not shown]
4.2.12 Currently participating and receiving study therapy or has participated in a study of an investigational agent and received study therapy or used an investigational device within 4 weeks of the first dose of entinostat.

4.2.13 Subject is receiving prohibited medications or treatments as listed in section 5.5 of the protocol that cannot be discontinued/replaced by an alternative therapy.

4.2.14 Prior treatment with HDACi for their melanoma.

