1.4.5 Preclinical Evidence about the Role of Histone Deacetylation Inhibition in Melanoma

Treatment with a pan-HDACi (LBH589) enhanced survival and proliferation of tumor antigen-specific T cells and suppressed the T regulatory (Treg) population when coadministered with gp100-specific T cells in a B16 melanoma model⁷⁹. The pan-HDACi lost its antitumor effect in immunodeficient as opposed to immunocompetent mice⁷⁰. Concurrent LBH589 (15mg/kg, M-W-F) and PD-1 blockade (3mg/kg, Tu-Th) in C57BL/6 mice showed delayed growth and enhanced survival of B16-F10-bearing melanoma tumors⁶⁹, similar to results seen in a lung adenocarcinoma model⁸³. Entinostat has effects in MDSC^{82,84}, Treg⁸¹, and dendritic cells⁸⁵. When administered as a single-agent orally no antitumor responses were seen in patients with metastatic melanoma⁸⁶.

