5.5 Prohibited Medications/Treatments

Subjects with pre-existing hypersensitivity to pembrolizumab or other PD-1/PD-L1 pathway inhibitors are disqualified from participation in the trial.

Subjects are prohibited from receiving the following therapies during the Screening and Treatment Phase (including retreatment for post-complete response relapse) of this trial:

- Antineoplastic systemic chemotherapy
- Targeted therapy (e.g. MAPK inhibitors), or biological therapy
- Immunotherapy not specified in this protocol
- Radiation therapy to multiple lesions or major surgery

Note: Radiation therapy or minor surgery to a single pre-existing but currently growing symptomatic extracranial lesion may be considered on an exceptional case-by-case basis after consultation with SYNDAX. The patient must have

measurable disease outside the radiated or operated field. Administration of palliative radiation therapy to a new lesion will be considered clinical progression.

- Live vaccines within 30 days prior to the first dose of trial treatment and while participating in the trial. Examples of live vaccines include, but are not limited to, the following: measles, mumps, rubella, varicella/zoster, yellow fever, rabies, BCG, and typhoid vaccine.
- Systemic glucocorticoids with the exceptions specified in section 4.2.1,
- Any other HDACi, including valproic acid,
- DNA methyltransferase inhibitors,
- Any additional anticancer agents, such as chemotherapy, immunotherapy, targeted therapy, biological response modifiers will not be allowed, even if utilized as treatment of non-cancer indications,
- Any other investigational agents.
- Traditional herbal medicines; these therapies are not fully studied and their use may result in unanticipated drug-drug interactions that may cause or confound the assessment of toxicities.
- Sensitive substrates of CYP1A2, CYP2C8, CYP3A with a narrow therapeutic window (see [APPENDIX A PROHIBITED MEDICATIONS](#)),
- Drugs that are known to inhibit or induce P-gp (see [APPENDIX A PROHIBITED MEDICATIONS](#)).

There are no prohibited therapies during the Post-Treatment and Follow-up Phases.

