6.3.6 Disease Assessment

This following test should be performed for assessment of melanoma disease.

6.3.6.1 Computed tomography (CT) of the whole body i.e., neck (if applicable), chest, abdomen, pelvis with IV contrast (or abdominal/pelvis MRI if allergy to IV contrast)

Baseline (screening) disease assessment should be obtained within 21 days of initiating study treatment. During the study, scans will be repeated as outlined in the Time and Events table in section 7.1 (i.e., at the end of week 10[D1 of cycle 4 or Study day 64/Wk10], end of week 15 [D1 of cycle 6 i.e., Study day 106/Wk16], end of week 21 [D1 of cycle 8 or Study day 148/Wk22], and end of week 27). Scans obtained during study treatment may be performed within ± 7 days of the scheduled study visit.

6.3.6.2 *Magnetic Resonance Imaging (MRI) of the brain*

MRI of the brain must be obtained at baseline (screening) and at end of treatment (i.e., at time of disease progression or at week 27); on any other visit **only if clinically indicated**, as per standard of care. If brain MRI is not feasible, patient can have a CT scan with IV contrast.

6.3.7 **Pre-Screening Pathology Assessment Period (pre-screening only)**

Given the limited 21-day screening period, and the requirement for absent TIL/TAL in melanoma tissues, archival metastatic tissue (locoregional, distant metastatic) can be requested and assessed before study enrollment (pre-screening). There is not an official pre-screening period given that [name], study's pathologist, is UNC's sole melanoma pathologist and routinely signs off his pathology reports, either from outside consultation slides or from in-house cases, along with a report about the presence of absence of tumor-infiltrating/-associated lymphocytes. If not available already, representative tumor sections from archived tumor blocks will be stained with H&E and will be assessed by [name], study pathologist, for assessment of quality using these criteria: (1) the tumor surface area must be at least 1cm² (which can be from a combination of metastatic blocks if necessary), (2) no more than 20% of necrosis, (3) the ratio of viable tumor cells to tumor-associated stroma should be at least 60/40, and (4) if TILs are present based on H&E stained sections, they must be $\leq 1\%$ of the total number of cells in the specimen; the amount of tissue should be ≥ 1 cm².

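### Exclusion 4.2.11 joins lesion number and size in one limb, so as worded it does not exclude untreated asymptomatic brain metastases that its own exception implies are excluded

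*Combined protocol and SAP*

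**What the plan says.** Section 4.2 opens with "All subjects meeting any of the exclusion criteria at baseline will be excluded from study". Criterion 4.2.11 then covers known, previously untreated parenchymal brain metastases and has three limbs joined by and/or: symptoms; number and size; and a need for antiepileptics or systemic corticosteroids for intracranial symptoms. The second and third limbs read "and/or more than one lesion with the largest diameter being > 5-mm and/or require antiepileptic drugs or systemic corticosteroids".

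Two exceptions follow. One is for previously treated, stable metastases, which is a different population. The other is for untreated disease: "Patients with active (i.e. not treated with stereotactic radiosurgery), single, asymptomatic, up to 5-mm in largest diameter brain metastases", measured within 2 weeks before the first entinostat dose.

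No other section sets a number or size limit for untreated brain lesions. Criterion 4.2.6 lets the investigator exclude a patient where taking part "is not in the best interest of the subject to participate, in the opinion of the treating investigator". Section 10.3 requires eligibility to be confirmed with the study coordinator before registration. Section 10.5.2 allows no single-subject eligibility exceptions.

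**The concern.** The second limb ties number to size, so both must be met. The exception describes a patient who is inside both limits. The complement of that exception is a patient outside either limit, and the limb does not say that. For a single larger lesion, or for several small ones, the exclusion and the exception therefore give different answers on the same scan. Because eligibility waivers are barred, one reader could enrol a patient whom another would call ineligible.

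What is at stake is patient safety, for two reasons specific to this trial:

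- Pembrolizumab starts only on day 22. Days 1 to 21 are entinostat alone, of which section 1.4.5 says: "When administered as a single-agent orally no antitumor responses were seen in patients with metastatic melanoma". The brain-metastasis experience in section 1.5.2 (18 patients, asymptomatic lesions up to 20 mm) is with pembrolizumab.
- Section 6.3.6.2 states "MRI of the brain must be obtained at baseline (screening) and at end of treatment", and otherwise only if clinically indicated. The scheduled on-treatment CT covers neck (if applicable), chest, abdomen and pelvis, not the brain.

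**Working it through.** The plan states no figure to reproduce. The check is one of logic.

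**Scope.** Untreated and asymptomatic, with no antiepileptics or steroids needed. The first and third limbs are then not met, and only number and size decide. Let n be the number of lesions and d the largest diameter in mm.

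**Rules**

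- Limb as written: excluded if n > 1 AND d > 5.
- Listed exception: allowed if n = 1 AND d ≤ 5.
- Reworded limb: excluded if n > 1 OR d > 5.

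**Grid.** The grid is my choice, for illustration: n = 1, 2, 3 and d = 4, 5, 6, 15, 25, giving 3 × 5 = 15 cells.

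| n | d | Limb as written | Within listed exception | Reworded limb |
|---|---|---|---|---|
| 1 | 4, 5 | not excluded | yes | not excluded |
| 1 | 6, 15, 25 | not excluded | no | excluded |
| 2 or 3 | 4, 5 | not excluded | no | excluded |
| 2 or 3 | 6, 15, 25 | excluded | no | excluded |

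- As written: excluded 2 × 3 = 6, passed 15 − 6 = 9.
- Listed exception: 1 × 2 = 2.
- Passed but not listed: 9 − 2 = 7, namely 3 single-lesion cells above 5 mm and 2 × 2 = 4 multiple-lesion cells at 5 mm or less.
- Reworded: passes the same 2 cells as the exception, so 0 conflict.

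The limb could also be read per lesion, as at least two lesions each above 5 mm. Those 7 cells still pass, and so do mixed cases such as 15 mm plus 4 mm.

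**What the exception shows about intent.** Under the literal limb, a single asymptomatic lesion of 5 mm or less is never excluded, so the exception removes nobody from the exclusion. It has work to do only if the base rule excludes by number or by size. The third limb hardly changes this, because it concerns drugs needed for intracranial symptoms and the exception is for asymptomatic patients.

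**Brain imaging interval.** Without progression or a clinical indication, the next required brain MRI is at week 27, about 27 × 7 = 189 days after day 1. Counted from a scan at the edge of the 21-day screening window this is 189 + 21 = 210 days. For the listed profile, measured within 2 weeks of the first dose, it is at most 189 + 14 = 203 days.

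**The case against.** The strongest reply is that this is loose drafting with an inferable meaning. Read as a whole, 4.2.11 points to a single lesion of at most 5 mm, and a careful investigator would apply it that way. The screening MRI shows the lesion, 4.2.6 permits exclusion on judgement, and a coordinator at the centre confirms eligibility before registration. Planned enrolment is only 14. The entinostat run-in and the MRI schedule also apply to the clearly permitted patient with one small lesion, so they are not harms created by the wording. All of this stands, and it keeps the point modest. It does not make the limb say what the exception implies, and no other section supplies the missing limit.

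A reader might infer three stronger things that the documents do not support:

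- *That the intended limit is unknown.* The redundancy of the exception points to exclusion by number or size.
- *That a patient whose brain lesion grows could not be treated.* Section 5.5 does confine the on-treatment local-therapy allowance to extracranial disease ("Radiation therapy or minor surgery to a single pre-existing but currently growing symptomatic extracranial lesion may be considered") and lists as prohibited "Systemic glucocorticoids with the exceptions specified in section 4.2.1". But section 5.4 allows treatment needed for the patient's welfare, and sections 5.3.2 and 5.6 direct corticosteroids for immune-related events. Progression ends study treatment (5.2, 5.8), and 5.5 prohibits nothing after treatment.
- *That such a patient goes unwatched for 189 to 210 days.* History, examination, performance status and toxicity are assessed on day 1 of every 21-day cycle. Brain MRI is available whenever indicated. Body CT at weeks 10, 16 and 22 may show progression, which brings forward the end-of-treatment MRI.

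**Conclusion.** The point holds as an inconsistency in an operative eligibility rule. As worded, 4.2.11 does not exclude untreated, asymptomatic brain metastases consisting of one lesion above 5 mm or of several lesions all of 5 mm or less, although its only untreated exception implies that both are excluded. It should be corrected, but its safety weight is modest given the mitigations above.

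The 7 of 15 cells show where the two rules disagree. They are not a patient frequency: the grid is illustrative and the documents give no rate for such patients. Nor do the documents show that a larger single lesion is unsafe, since section 1.5.2 describes pembrolizumab as safe in 18 patients with lesions up to 20 mm. Those data do not cover the entinostat-only weeks.

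The conclusion rests on the literal conjunction in the limb and on the scope stated in the working. Sample size, alpha, power and the planned analyses are unaffected.

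**What to change.** Reword the second limb of 4.2.11 to: *more than one lesion, and/or any lesion > 5 mm in largest diameter*. It then matches the listed exception exactly, including at 5 mm.

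The cost is one line in an amendment. The downside is that a few patients with untreated brain lesions become clearly ineligible in a small trial. If the sponsor's clinicians do want to admit a larger single lesion, that limit should be stated in both the limb and the exception.

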5.0 TREATMENT PLAN

5.1 Schema

Eligible subjects must have histologically confirmed AJCC stage III/IV melanoma of any subtype and sufficient, archived metastatic tumor tissue to confirm absence

of TIL/TAL in representative H&E-stained tumor tissues. Subjects are eligible even if they have received any prior PD-1/PD-L1 pathway inhibitors or any other systemic treatments, including immunotherapies, on condition that they have not received HDACi for their melanoma. They must have recovered from any side effects associated with prior anticancer treatments. Patients will be 'primed' with entinostat, 5mg PO qwk, for 3 weeks. In the end of cycle 1, beginning of cycle 2 (day 22±2 days), immediately before concurrent entinostat-pembrolizumab treatment, they will undergo a mandatory melanoma biopsy after which they will receive up to 4 infusions of standard of care pembrolizumab along with weekly administration of entinostat. Restaging radiographic studies will be performed on week 10 and then every 6 weeks until week 27. Peripheral blood will be collected at baseline; in the end of cycle 1, beginning of cycle 2 (day 22±2 days), immediately before concurrent entinostat-pembrolizumab treatment; on week 10 after 3 infusions (cycles) of pembrolizumab; and at the end of treatment, either at disease progression or week 27, or if intolerable toxicity occurs that requires permanent discontinuation of pembrolizumab and/or entinostat. Subjects will be considered to have completed all trial requirements if:

- (a) Their disease has progressed by RECIST v1.1 criteria within less than 10 weeks from the first dose of entinostat,
- (b) They develop toxicity related to pembrolizumab or entinostat, but still complete sample collection (peripheral blood and tumor tissue) and tumor assessments by at least week 3,
- (c) Complete the entire 27 weeks of combination therapy and study-related assessments without experiencing disease progression by RECIST v1.1 criteria or clinical grounds. Those subjects experiencing clinical benefit after 27 weeks may continue pembrolizumab therapy per standard of care.

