5.2 Treatment Dosage and Administration

Subjects in this trial will be administered entinostat, 5mg PO, once weekly (D1, D8, D15 of a 21-day cycle) starting on day 1 of study treatment. Pembrolizumab, 200 mg will be administered intravenously (IV) every 3 weeks and initiated at cycle 2 after the mandatory research tumor biopsy in the end of cycle 1, beginning of cycle 2 (day 22±2 days). Combination therapy with both agents will continue if subject is receiving clinical benefit from therapy for up to 27 weeks (8 cycles of combination therapy or approximately 6 months). Study therapy will be discontinued for intolerable toxicity, disease progression or for other reasons at the discretion of the investigator.

Agent	Required Premedications; Precautions	Dose	Route	Schedule	Cycle Length
Entinostat	Take on an empty stomach i.e., at least 2 hours after a meal and at least 1 hour before the next meal.	5 mg ³	Oral (PO)	Start on study D1 of cycle 1 and administer once weekly (i.e., D1, D8, D15 of each cycle) for 9 cycles qwk) (±1 day)	Every 21* days
Pembrolizumab	Risk for immune-mediated ¹ and infusion-related ² reactions	200 mg ³	IV; administer over 30 min (range -5, +10 min)	Start on study D22 (± 2 days) of the study (i.e., D1 of cycle 2) and administer every 21 (± 2) days (q3wk) x 8 cycles (i.e., cycles 2-9)	

1. See Section 5.3.2 for management guidelines for immune-mediated AEs.
2. See Section 5.6.1 for management guidelines for infusion-related AEs
3. On days when entinostat is administered on the same day as pembrolizumab, entinostat should be taken before the pembrolizumab infusion.

*Entinostat monotherapy for cycle 1 and combination therapy should be initiated on D1 of cycle 2 and continue until withdrawal for toxicity, withdrawal for patient preference, disease progression or the subject completes 27 weeks of protocol-directed therapy. Entinostat cannot be continued beyond the 27-week duration of study-directed therapy for the trial, irrespective of treatment response.

*Pembrolizumab will be started on D22 of the study (i.e., D1 of cycle 2) and may continue for up to 24 weeks in combination with entinostat (i.e. cycles 2-9). Following completion of the trial therapy at 27 weeks and on condition that there is no disease progression, pembrolizumab can be continued per investigator discretion, as per standard of care guidelines.

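### Section 5.1 caps pembrolizumab at 4 infusions while the dosing schedule gives 8, and its wording leaves open whether the week-10 blood sample follows 2 or 3 infusions

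*Combined protocol and SAP*

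**What the plan says.** Section 5.1 (Schema), the opening text of the treatment plan, states that after the mandatory biopsy patients get "up to 4 infusions of standard of care pembrolizumab" together with weekly entinostat. The same section lists the ways in which a subject counts as having met all trial requirements. Item (c) begins "Complete the entire 27 weeks of combination therapy". It also places one of the blood samples "on week 10 after 3 infusions (cycles) of pembrolizumab".

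Section 5.2 describes the treatment period as "8 cycles of combination therapy or approximately 6 months". Its dosing table starts pembrolizumab on day 22 and reads "administer every 21 (± 2) days (q3wk) x 8 cycles (i.e., cycles 2-9". A footnote to that table says that pembrolizumab "may continue for up to 24 weeks in combination with entinostat (i.e. cycles 2-9".

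The dosing schema in 5.2.1 marks pembrolizumab on days 22, 43, 64, 85, 106, 127, 148 and 169. The visit lists in 7.4.2 to 7.4.7 contain a 200 mg dose at each of those visits. The synopsis (1.1) also gives the combination in cycles 2 to 9.

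**The concern.** Section 5.1 is current treatment-plan text, and its wording sets a ceiling. A site that follows it would give no infusion after the fourth. A site that follows 5.2 would give up to eight. Section 10.5 requires conduct to follow the approved protocol to the letter, so either course departs from some operative passage.

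The number of infusions fixes the planned exposure behind two secondary endpoints: the 27-week PFS rate and the toxicity of the combination. If sites differed on this, those summaries would mix two regimens in about 10 evaluable patients.

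The blood-sample wording raises a smaller question. Section 9.3.5 compares week 10 with baseline to describe the change under combination treatment. To interpret that contrast, a reader needs to know how many infusions came before the sample.

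**Working it through.** **Inputs.** Cycle length is 21 days (5.2). The first pembrolizumab dose is on day 22, day 1 of cycle 2 (5.2). Pembrolizumab is given in cycles 2 to 9 at 200 mg (5.2, 5.2.1). Week 10 starts on day 64, day 1 of cycle 4 (5.2.1, 7.4.4). Week k covers days 7(k−1)+1 to 7k (note under the Time and Events Table).

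**The schedule's own count.** Day 1 of cycle c is 1 + 21(c−1). For c = 2 to 9 this gives days 22, 43, 64, 85, 106, 127, 148 and 169. That is 8 infusions, as 5.2 states, and the days match the schema in 5.2.1.

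**Four against eight.**

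| | 5.1 cap | 5.2, 5.2.1, 7.4 |
|---|---|---|
| Infusions | 4 | 8 |
| Last infusion | 22 + 3×21 = day 85 | 22 + 7×21 = day 169 |
| Last day of that cycle | 85 + 20 = day 105 (105/7 = week 15) | 169 + 20 = day 189 (189/7 = week 27) |
| Weeks of combination | 4×3 = 12 | 8×3 = 24 |
| Maximum planned dose | 4×200 = 800 mg | 8×200 = 1,600 mg |

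The last infusions are 169 − 85 = 84 days (12 weeks) apart.

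**Can any reading reconcile them?** Adding the entinostat-only cycle to four combination cycles gives 3 + 12 = 15 weeks, not the 27 in completion rule (c). Three other places also run past a fourth infusion in cycle 5:
- The delay rules in 5.3 cover infusions at cycles 7, 8 and 9.
- Section 5.8 sets the maximum at 9 cycles.
- Section 7.4.7 lists doses at weeks 19, 22 and 25.

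**The week-10 sample.** Infusions before day 64 fall on days 22 and 43, so there are 2. Counting day 64 itself, there are 3. Week 10 runs from day 64 to day 70, so the third infusion is due on its first day. The words in 5.1 can therefore be met by a draw taken after that day's infusion. Against this, the bracketed reference to cycles suggests three completed pembrolizumab cycles, and only cycles 2 and 3 are complete by day 64. Section 7.4.4 lists the blood draw as part of item 4 and pembrolizumab as item 9, but does not say that the list is a sequence.

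**Primary endpoint.** Conversion is read from the day-22 biopsy, taken before any pembrolizumab. The rule of at least 3 of 10 has an exact type I error of 0.0401 at a true rate of 0.08 and power of 0.8327 at 0.4. These match the stated 0.04 and 83%, and neither depends on the number of infusions.

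**The case against.** The strongest reply is that the protocol tells sites where to look for dosing, and it is not 5.1. Footnote 7 of the Time and Events Table sends both drugs to 5.2 and 5.2.1, and the note under the dosing schema ties administration to the weeks shown there. The synopsis, dosing table, schema, visit lists, delay rules and duration section all run to cycle 9. A site would have to follow one narrative phrase against all of them for the 12-week difference to occur. This stands, and it limits the practical effect. It does not remove the contradiction, because 5.1 still states a cap that the other sections exceed.

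Three stronger readings are tempting, and the documents do not support them.

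- **A flat contradiction of 3 against 2 infusions at week 10, with exposure one third lower than stated.** The text dates the sample on week 10 after 3 infusions. It does not say that all 3 come before week 10, and the third is due on day 64. This is an ambiguity about the order of draw and infusion.
- **Doubt about the exposure behind the week-10 response.** In 5.1 the phrase about 3 infusions belongs to the blood collection only. The restaging sentence gives no infusion count. Objective 2.2.1 times response after 3 cycles of study treatment, 3×21 = 63 days or 9 weeks. That fits one entinostat-only cycle plus two combination cycles and agrees with the schedule.
- **Damage to the primary analysis.** The endpoint is assessed before the first infusion.

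**Conclusion.** The main point holds as an internal inconsistency, wrong as written: 4 infusions in 5.1 against 8 in the synopsis, 5.2, 5.2.1 and 7.4. Its literal size is 84 days between last infusions, or 12 weeks of combination against 24. That is an upper bound and not an expected effect. It assumes that a site obeys the 5.1 cap despite the footnote directing dosing elsewhere, and that doses fall on their nominal days. Under that assumption the 27-week PFS rate and the toxicity data would describe a different planned exposure.

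The week-10 wording is a lesser and separate point. The sample may follow 2 or 3 infusions, and the protocol does not say which. Only the exploratory blood comparison of week 10 with baseline is affected. The week-10 response, the day-22 primary endpoint and the design's error rates are not.

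The correction should be made because it is specific and almost free, although most of the protocol already agrees on one schedule.

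**What to change.** Two changes are needed.

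1. Reconcile the number of pembrolizumab infusions in 5.1 with the synopsis, 5.2, 5.2.1, 7.4 and completion rule (c), so that one maximum appears everywhere. Which count is right is for the sponsor and the investigator to decide.
2. Reconcile the blood-draw wording in 5.1 with 7.4.4, stating whether the week-10 sample is taken before or after that day's infusion. Use the same description in 6.5.1 and 9.3.5, so that the week-10 versus baseline contrast has a defined prior exposure.

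The cost is two phrases in 5.1 and matching clarifications of sample timing in a future amendment. The sample size, the decision rule and the visit schedule need no change on account of the wording. If patients have already been treated, the report should tabulate infusions received per patient, and whether each week-10 sample preceded or followed the infusion.
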